### **6.3. Randomization**

Subjects will be randomly allocated to dosing group according to a pre-specified randomization scheme prepared by an independent statistician. Once confirmed eligible for the study, subjects will be randomized using a computerized IWRs system to filgotinib 200 mg or placebo in a 1:1 ratio.

Randomization will be stratified according to the type of rheumatic condition (RA or Spondylarthritis [PsA, AS, nrAxSpA]), concurrent use of MTX (yes or no) and sperm concentration measured at Screening (“Baseline”) according to the following strata:

- 15 to 25 million/mL
- > 25 to 50 million/mL
- > 50 million/mL

### **6.4. Double-blind Treatment Phase (Day 1 Through Week 13 Study Visit)**

All subjects will receive blinded study drug until completion of all Week 13 assessments.

Study assessments will be completed as specified in the Study Procedures Table ([Appendix 2](#)).

Invasive study procedures such as blood draws should be done at the end of a study visit, as much as possible.

The end of the Double-Blind Treatment Phase is when the Week 13 semen results are available to the investigator and have been evaluated. Based on this evaluation, subjects are assigned to enter the Monitoring Phase or the Extension Phase.

## **6.5. Extension Phase**

In the Extension Phase, subjects will receive open-label treatment (filgotinib or Standard of Care) and have a study visit every 13 weeks that includes semen analysis. The first scheduled visit of the Extension Phase occurs at Week 26.

In case sperm parameters at any visit (including Week 156) meet any of the pre-specified decrease thresholds, subjects will enter the Monitoring Phase.

During the Extension phase, Standard of Care and concomitant treatment may be optimized at the discretion of the investigator taking into consideration the protocol restrictions (see Section 5.3).

In case a subject needs to be treated with a prohibited medication to control their rheumatic condition (see [Table 5-1](#)), the subject will discontinue the study and complete an ET visit (including semen collection). For subjects on filgotinib, this will be followed by a safety follow-up visit 30 days after last study drug dose.

All subjects who did not enter the Monitoring Phase will continue the study until the Week 156 visit.

Subjects with newly positive (converted) QuantiFERON® [or centrally reported equivalent assay] TB test should be discontinued from study drug. Subjects who were previously treated for TB with a complete and adequate course of therapy as per local standard of care and as verified by the investigator do not need to have yearly QuantiFERON® tests. Subjects previously treated for TB should be screened at least yearly for signs and symptoms consistent with reactivation of TB. Any subject with active TB should be discontinued from the study.

Study assessments will be completed as specified in the Study Procedures Table ([Appendix 2](#)).

## **6.6. Monitoring Phase**

Subjects on filgotinib who enter the Monitoring Phase will discontinue study drug and start Standard of Care. Subjects on Standard of Care will continue treatment.

All subjects who enter the Monitoring Phase will undergo semen evaluations every 13 weeks starting from their entry into the Monitoring Phase, for up to 52 weeks or until Reversibility (see [Definition of Terms](#)) is met, whichever is achieved first.

Study assessments will be completed as specified in the Study Procedures Table ([Appendix 2](#)).

## **6.7. Early Termination**

Subjects who discontinue study participation for any reason prior to Week 156 in the Extension Phase, prior to reaching Reversibility or Week 52 in the Monitoring Phase (whichever occurs first) will complete an ET Visit. Subjects on blinded study drug or open-label filgotinib will also undergo a routine safety follow-up visit 30 days ( $\pm 5$  days) after the last dose of study drug.

## **6.8. Safety Follow-Up Visit 30 Days Post Dose ( $\pm 5$ days)**

All subjects will complete a safety follow-up visit 30 days after the last dose of study drug (blinded [filgotinib or placebo] or open-label [filgotinib]).

Study assessments will be completed as specified in the Study Procedures Table ([Appendix 2](#)).

## **6.9. Safety and Tolerability**

AEs, PE, vital signs, ECGs, and laboratory assessments (standard hematology, serum/plasma chemistry, and urinalysis) will be collected. Semen samples will be collected in accordance with Section [6.11](#).

### **6.9.1. Thromboembolic Events**

Subjects experiencing a thromboembolic event should be evaluated for the overall risk of recurrent thromboembolism and referred to a specialist for further testing as appropriate (including but not limited to evaluation for an underlying inherited hypercoagulable state).

## **6.10. Clinical Laboratory Evaluations**

The hematology and serum chemistry laboratory analyses will be performed at a central laboratory. Reference ranges will be supplied by the central laboratory and will be used by the investigator to assess the laboratory data for clinical significance and pathological changes.

Blood samples will be collected by venipuncture in the arm at the time points indicated in the Study Procedures Table ([Appendix 2](#)). In addition, urine samples for the clinical laboratory assessments will be collected. Subjects only need to be fasted on days where lipid profiling is scheduled.

Please refer to [Appendix 11](#) for table of clinical laboratory tests.

The laboratory values outside the normal range will be flagged and clinical relevance will be assessed by the investigator. More frequent sampling as well as additional tests may be performed as deemed necessary by the investigator as indicated.

Note that in the case where clinically significant laboratory test results are a potential reason for discontinuation from the study drug and withdrawal from the study, retesting of the affected parameter(s) should be prompt (within 3 to 7 days) after the investigator has consulted with the Sponsor Medical Leader or designee. A decision regarding subject discontinuation should be made after the results from the retest are available (see Section [3.7](#) for additional information).

The details of sample handling and shipment instructions will be provided in a separate laboratory manual.

## 6.11. Semen Collection Procedure

At each of the following time points, subjects will provide 2 separate semen samples collected within a 14-day period. Each semen sample must be collected with a  $\geq 48$  hours and  $\leq 7$  days ejaculation free period at the following time points.

- Screening (Baseline)
- After the Double-blind Treatment Phase (Week 13 study visit)
- Every 13 weeks during the Extension Phase
- Every 13 weeks during the Monitoring Phase
- At the Early Termination Visit

[figure not shown]
The 2 time-points for the semen sample collection will be scheduled in agreement with the investigator on the study visit day and/or as soon as possible after the visit day.

All decisions of retesting any semen/sperm parameter (i.e. obtaining a third sample at any of the above time points), must be approved by the Sponsor Medical Leader or designee before the retest. Such inquiries will only be considered in select instances where the semen sample with the questioned value(s) is found to be non-assessable or invalid (e.g. collection without adherence to ejaculation-free period; intercurrent illness or dehydration at time of collection; incomplete capture of semen sample; and/or sample processing or semen analysis that deviates from standardized procedure). The third semen sample, when indicated, must be collected within 14 days of the prior sample and with an ejaculation free period of  $\geq 48$  hours and  $\leq 7$  days (See [Figure 6-1](#)).

At each time point, the mean of 2 separate semen samples for each parameter will be used for the assessment of study eligibility, entry into the Extension Phase, entry into the Monitoring Phase, and exit from the Monitoring Phase.

The results of the semen analysis will be evaluated and discussed with the subject and he will be informed about the appropriate next steps to be taken in the study.

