JAK inhibition is expected to increase the risk of infection based on mechanism of action. Across the global studies in filgotinib, in general, active treatment arms have increased incidences of infection versus placebo. In the present protocol, treatment interruption and discontinuation considerations surrounding infections are incorporated, and sites and investigators will be trained regarding such circumstances. All subjects will be screened for TB, and subjects with active infections will be excluded. Malignancy has been reported in subjects on filgotinib; in the present study, subjects with recent malignancies will be excluded as outlined in the inclusion criteria. For further details about infections and malignancies, please reference the IB.

The potential benefits of JAK inhibition include improvement in clinical symptoms. JAK inhibition may be efficacious in the treatment of RA, PsA, AS and nrAxSpA based on results from the Phase 2 studies of subjects with PsA, and AS. Filgotinib is currently in Phase 3 studies for RA.

Overall, clinical findings and laboratory changes associated with filgotinib are consistent with JAK 1 inhibition. Based on Phase 2 and Phase 3 data the expected benefit of using filgotinib as proposed in this study is considered to outweigh any associated risks. In addition, the subject population in the present study will consent to a risk of potentially permanent infertility, thus individual male subjects in conjunction with the treating physician may evaluate the benefit-risk profile of filgotinib. A lack of response contingency from Week 13 onward in the current study, targeting arthritis Non-responders at Week 13, will enable early access to active drug or Standard of Care treatment when clinically indicated. This rescue approach, the provision of best supportive care during the extension phase, and the limited study duration, makes the use of placebo ethically acceptable for the specified duration.

An external multidisciplinary Data Monitoring Committee (DMC), including an expert in male fertility, will be appointed to monitor the study.

The DMC has monitored the study until the date of protocol amendment 2, including the data for the second unblinded interim analysis (IA2). As of amendment 2, the DMC will be

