#### 5.1.1. Blinding

During the randomized Double-blind Treatment Phase, subjects and all personnel directly involved in the conduct of the study will be blinded to treatment assignment. Specified personnel not directly involved in the study conduct may be unblinded based on their study role. Study drug will be dispensed by the study pharmacist, or designee, in a blinded fashion to the subjects. The Pharmacokinetics File Administrator, or designee, in Bioanalytical Operations and/or Clinical Data Management, who facilitates the data transfer of PK files between the Sponsor and vendors, will remain unblinded. Individuals in Clinical Packaging & Labeling or Clinical Supply Management who have an Unblinded Inventory Manager role in the IWRS system for purposes of study drug inventory management will remain unblinded. Individuals responsible for safety signal detection, Investigational New Drug (IND) safety reporting and/or expedited reporting of suspected unexpected serious adverse reactions (SUSARs) may be unblinded to individual case

data and/or group level summaries. External (ie, contract research organizations [CROs]) biostatisticians and programmers will be unblinded to produce tables, figures, and listings for unblinded review at DMC meetings, and the external biostatistician will serve as the external statistician to the DMC. Regulatory Quality and Compliance personnel in Research and Development may also be unblinded for purposes of supporting Quality Assurance activities and/or Regulatory Agency inspections.

For ongoing subjects, the study teams and study staff at the sites and all other staff directly involved in the conduct of the study will remain blinded to the double-blind phase treatment assignments until the final analysis when the database has been locked. Publication of the IA2 data is planned by the Sponsor. This publication will contain group level data for the entire study population, but will unblind the study teams and staff directly involved in the conduct of the study to the individual baseline treatment assignment of subjects who completed the study before IA2.

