#### **5.1.2. Procedures for Breaking Treatment Codes**

After Week 13 of the Double-blind Treatment Phase, subjects who are Arthritis Responders and whose sperm parameters do not meet any of the pre-specified decrease thresholds will be unblinded by the IWRS system and enter the Extension Phase.

Blinding of study treatment until the Week 13 visit is critical to the integrity of this clinical study. Therefore, treatment assignments should remain blinded until the semen analysis results related to the Week 13 visit are known, unless that knowledge is necessary to determine emergency medical care for the subject. In the event of a medical emergency where breaking the blind prior to completion of the Week 13 visit procedures is required to provide medical care to the subject, the investigator may obtain the individual subject treatment assignment directly from the IWRS system. The Sponsor recommends, but does not require, that the investigator contacts the Sponsor Medical Leader or designee before breaking the blind.

The investigator however must contact the Sponsor Medical Leader or designee promptly after unblinding prior to the Week 13 visit. The rationale for unblinding must be clearly explained in source documentation and on the eCRF, along with the date on which the treatment assignment was unblinded. If a subject's treatment assignment is disclosed to the investigator, the subject will have study drug discontinued. All subjects will be followed until study completion unless consent to do so is specifically withdrawn by the subject.

The Sponsor may independently unblind cases prior to the Week 13 visit for expedited reporting of SUSARs to Regulatory Authorities.

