- Semen collection (2 separate collections in accordance with Section 6.11) and record date and time of last ejaculation prior to sample. Semen collection should be collected to coincide with Day 1 (Baseline visit) as much as possible.
- Disease Specific scales and questionnaires

*A single retest of any exclusionary screening lab (non-semen samples) is permitted:*

- at the discretion of the investigator, if the initial exclusionary value is invalid due to a documented error in sample collection or laboratory processing, OR
- upon the approval of the Sponsor Medical Leader or designee, if there is an extenuating circumstance around the exclusionary value.

Retesting of exclusionary parameters in Screening semen samples is discussed in Section 6.11.

*Subjects meeting all of the inclusion criteria and none of the exclusion criteria will return to the clinic after Screening, for randomization into the study.*

From the time of obtaining informed consent through the first administration of IMP, record all SAEs, as well as any AEs related to protocol-mandated procedures on the AEs case report form (CRF/eCRF). All other untoward medical occurrences observed during the Screening period, including exacerbation or changes in medical history are to be captured on the medical history CRF/eCRF. See Section 7 Adverse Events and Toxicity Management for additional details.

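### Protocol 6.11 lets a post-baseline semen sample be replaced after its value is questioned, with no visible rule that validity be judged without sight of that value, so a true harm signal can be shrunk

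*Protocol*

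**What the plan says.** Protocol 6.11 (with the same rule in the Synopsis and 3.4) asks for two semen samples at each time point and uses their mean for all decisions. On a third sample it says: "Such inquiries will only be considered in select instances where the semen sample with the questioned value(s) is found to be non-assessable or invalid". The examples of invalidity include "intercurrent illness or dehydration at time of collection", with no severity, timing or evidence required. Each retest "must be approved by the Sponsor Medical Leader or designee before the retest". Concentration is read locally; only morphology is read centrally.

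Protocol 1.4 says "JAK inhibition is expected to increase the risk of infection based on mechanism of action" and reports that across filgotinib studies "active treatment arms have increased incidences of infection versus placebo". It gives no rates.

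On blinding, Protocol 5.1.1 says that in the double-blind phase "subjects and all personnel directly involved in the conduct of the study will be blinded to treatment assignment", and 5.1.2 says that "treatment assignments should remain blinded until the semen analysis results related to the Week 13 visit are known". Treatment after that is open-label (Protocol 3.2). A man who crosses a decrease threshold there stops filgotinib if he is on it and carries on with Standard of Care if he is not (Protocol 3.3).

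SAP 6.2 bases the Week 13 primary analysis on observed cases with two evaluable samples. SAP 3.7.3 mentions a supportive analysis that also admits men with a single evaluable sample. SAP 3.5.2 keeps outliers. None of these visible passages says what happens to a sample that was declared invalid and replaced.

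**The concern.** The wording starts from a value that someone has questioned, so the result can be known when validity is judged. Low values are the ones with consequences for the subject, and so the likeliest to be queried. The endpoint is a cut-off on the mean of two samples, so exchanging the lower sample for a fresh one will often remove the event.

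This matters if low values are replaced more often on filgotinib than on placebo. Under the blind that can happen in two indirect ways: the drug lowers sperm concentration, so that more filgotinib samples are low and open to question; or illness at collection is commoner on filgotinib. Both pull the difference toward no harm, which is the unwelcome direction in a safety trial.

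**Working it through.** **The plan's own figure.** Protocol 8.7 wants 100 evaluable men per group with 20% non-evaluable: 100 / (1 − 0.20) = 125 per arm, as stated.

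**Yardstick.** With 100 per arm and the same event rate p in both arms, the unstratified 95% half-width for the difference is 1.96 × √(2p(1 − p)/100). This gives 6.0 points at p = 5%, 8.3 at 10% and 11.1 at 20%.

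**Simulation set-up.** There were 500,000 men per arm with log-normal samples. An event is a mean of two post-baseline samples at or below 0.5 × the mean of two baseline samples. At most one sample is replaced per visit. The documents give no within-man variability, illness rate at collection or retest rate, so these are assumptions: within-man log SD 0.35 to 0.60; illness per sample 2% v 3%, 3% v 6% or 5% v 10% (placebo v filgotinib).

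**Step 1: low samples replaced under the blind, for reasons unrelated to illness.** With no drug effect, log SD 0.5 and half of low samples replaced, the event rate falls from 8.8% to 5.9% in both arms and the difference stays at zero. With a 30% drug effect:

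| Log SD | Low samples replaced | Difference before → after (points) | Share lost |
|---|---|---|---|
| 0.35 | 10% | 14.66 → 13.81 | 0.85/14.66 = 5.8% |
| 0.35 | 50% | 14.61 → 10.88 | 3.73/14.61 = 25.5% |
| 0.5 | 10% | 16.73 → 16.05 | 0.68/16.73 = 4.1% |
| 0.5 | 50% | 16.72 → 13.58 | 3.14/16.72 = 18.8% |
| 0.6 | 10% | 16.18 → 15.58 | 0.60/16.18 = 3.7% |
| 0.6 | 50% | 16.26 → 13.76 | 2.50/16.26 = 15.4% |

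The loss is about 4% to 26% of the true difference.

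**Step 2: only low samples taken during illness are replaced.** Change in the difference, in points, against keeping every sample:

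| Effect of illness on concentration | No drug effect | 30% drug effect |
|---|---|---|
| None | 0.0 to −0.4 | −0.3 to −1.0 |
| Halves it | −0.2 to −1.5 | −0.6 to −4.3 |

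**Step 3: is the trigger or the illness responsible?** If every sample taken during illness is replaced whatever its value, and illness does not affect sperm, the shift is at most 0.1 points. In the first row of Step 2, then, the damage comes from letting the value trigger the replacement. If illness halves concentration, replacing all illness samples shifts the difference almost as much as replacing only the low ones (−2.93 v −2.97 points at log SD 0.5, illness 5% v 10%, 30% drug effect). What is removed there is a decline caused by illness, and whether that should count is a choice of estimand.

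**The case against.** Much of the defence stands. Up to Week 13 the people concerned are blinded, a retest needs a finding of invalidity as well as sponsor approval, the rule is the same in both arms, and the sample is replaced, not simply dropped. A reader might infer that low values can be picked out of the filgotinib arm; for the primary endpoint the documents do not support that. Several grounds (abstinence, incomplete capture, processing deviations) can be checked without the result, and the wording suggests that retests are rare. Replacing a sample taken in acute illness is also a defensible way to isolate a direct testicular effect.

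Two other inferences fail. Protocol 6.2.1 says "Retesting of exclusionary parameters in Screening semen samples is discussed in Section 6.11", which might suggest that the same mechanism works at Screening. It does not: that replacement precedes randomisation, so it cannot be driven by assigned treatment, and replacing a low Screening value raises Baseline and makes a later 50% fall more likely. A reader might also infer that replaced values disappear from all analysis. That cannot be shown: the Semen Analysis Set definition and most of the sensitivity-analysis text are not in the copy reviewed, Figure 6-1 and the separate semen manual are not available, and nothing says that replaced results are deleted.

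What the defence does not answer is that no visible text blinds the person judging validity to the value. Blinding to treatment prevents deliberate selection by arm, but not the shrinkage in Step 1.

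**Conclusion.** The point holds as a correctable weakness in the sampling rule; it is not evidence of selective removal by arm. At Week 13, value-triggered replacement unrelated to illness gives no bias if filgotinib has no effect. If filgotinib lowers concentration by 30%, it loses about 4% to 26% of the true difference when 10% to 50% of low samples are replaced. The illness route alone is worth about 0 to 1.5 points with no drug effect. It reaches about 4 points only if illness is twice as common on filgotinib (10% v 5% of samples), halves concentration and coincides with a 30% drug effect. These shifts are smaller than the 6 to 11 point half-width of the interval, but they all run toward no harm. Every size rests on assumed variability, illness and retest rates.

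Questioning with knowledge of the arm is possible only in the open-label Extension Phase, from Week 26 onward, where only men on filgotinib lose study drug if a low value stands. The Week 26 proportion is summarised descriptively by treatment sequence and responder group (SAP 6.5.1), without a filgotinib–placebo contrast.

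**What to change.** In Protocol 6.11, have sample validity recorded from collection and laboratory records before the result is released, or judged by someone blind to both value and arm. State what counts as intercurrent illness, and retain every analysed result.

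In SAP 6.2, add a sensitivity analysis of the primary endpoint that uses the original two analysed post-baseline samples wherever the replacement was for illness or another reason that does not make the sample unmeasurable. Tabulate third samples by arm, visit and reason.

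The cost is one checklist field, one table and one extra analysis. The drawback is that the sensitivity analysis admits some noisier samples. Amendment 2 states that the study has passed its primary and secondary analysis time points, so the collection change can help only remaining visits. The table and sensitivity analysis can still be added, provided the original results were kept, and should be reported in the clinical study report as additions made after the SAP was finalised.
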